### 8.2.3 Stopping Rules

IMG-7289 will be discontinued in the event of the following:

- Post DLT, the Medical Monitor and Principal Investigator deem it unsafe for the patient to continue on IMG-7289.
- Post dose reduction due to DLT, the patient fails to demonstrate significant improvement within 21 days.
- Post temporary interruption of IMG-7289 due to platelet counts below  $25 \times 10^9/L$  (25 k/ $\mu$ L), the patient's platelet counts don't return to  $> 50 \times 10^9/L$  (50 k/ $\mu$ L) within 21 days.

Patients who discontinue IMG-7289 will enter follow-up assessments beginning with EoT visit.

CCI

## 9 STUDY ASSESSMENTS

This section provides comprehensive detail on the visits and assessments required; this section should serve as the main guidance for use during study visits. The Schedule of Assessments (Section 16.1) contains these details in schematic form, and is provided for use in a supportive/reference capacity only. In an effort to maintain clarity while facilitating a modicum of brevity, the 'Terms' in **Table 4** below will be utilized in this section to encompass the broader 'Protocol Meaning' as stated.

**Table 4: List of Protocol Terms and Meanings**

Term	Protocol Meaning
Limited Physical Exam, including Vital Signs	
 
• Spleen measurement - The edge of the spleen shall be determined by palpation, measured in centimeters, using a soft ruler/tape, from the costal margin to the point of greatest splenic protrusion. The spleen should be measured in the same manner at all visits.
 
• Vital signs, after patient has sat semi-supine for ~3 minutes, of:               
 
○ Heart rate
 
○ Respiratory rate
 
○ Temperature
 
○ Systolic/diastolic blood pressure
 
 
 
• Weight, measured (in kg)
 
• Review of body systems for changes from previous visit
 

Full Local Lab Assessment	Assessment consisting of the following test panels to be performed locally (see Section 10.1.1 for specific analytes required): 
 
• Haematology with manual differential
 
• Coagulation
 
• Biochemistry
 
• Urine or serum pregnancy test for women of child bearing potential (WOCBP); results to be reviewed prior to dosing, if applicable
 

Collect MPN-SAF TSS	MPN-SAF TSS is to be completed by the patient in their native language and in the format provided. The 24-HOUR RECALL tool will be completed daily for the 7 days preceding first dose (Days -6 to pre-dose Day 0) during Baseline. The 7-DAY RECALL tool will be completed weekly from Day 7 through the EoS Visit. Ideally, the 7-DAY RECALL version will be completed on the same time and day each week for consistency. On visit days, the MPN-SAF TSS should be completed prior to the study visit, and if the patient arrives without a completed MPN-SAF TSS, then it will be completed during the visit and collected prior to the patient departing. Importantly, multiple MPN-SAF TSS forms will need to be provided to the patient for completion between visits as visit frequency decreases to less than weekly. Date of completion should be documented on each MPN-SAF TSS completed.

Term	Protocol Meaning
Bone Marrow Sampling	
 
• Aspirate (sample taken from first pull, whenever possible, and no later than the second) and biopsy collected as per site standard procedure.
 
• A central laboratory will perform morphology review, myelofibrosis grading and genomic analysis (See Section 10.1.2).
 
• Note: Any results available from site routine work-up, including morphology, cytogenetics, other genetic interrogations will be collected for study purposes either via the eCRF or through collection of local reports.
 

Dosing Instructions	
 
• Instruct patients to refer to their Dosing Card every day, for details on IMG-7289 dosing and what to do if a dose is missed
 
• Take their IMG-7289 in accordance with Section 7.2.2
 
• Handle any missed IMG-7289 doses as per Section 7.2.5
 
• Bring all medication to every clinic visit, including empty bottles
 

Administer IMG-7289	Administer IMG-7289 with a glass of water, instruct patient to continue to fast for at least 30 minutes, and record the exact time of dosing.
Adverse Events and Concomitant Medications	Use non-directive questions (i.e., “How are you feeling”) to query patient re: any AEs that may have occurred. Also, inquire about medication changes since the last visit.

**Note:** If at any time additional clinical evaluation outside of the visit schedule is deemed necessary by the Investigator, then unscheduled visits should occur as appropriate.

### 9.1 Informed Consent

Patients must provide written informed consent before undergoing any study-related procedures. The Principal Investigator (PI), or designee, will explain to the patient the aims of the study, the risks and benefits involved and that their participation is voluntary. Each patient will acknowledge receipt of this information and that they wish to participate in the study by giving written informed consent for their involvement in the study in the presence of the PI, or designee, who will also sign and date the Participant Information Sheet/ Consent Form (PISCF). Time, date, name of the person taking consent and any questions raised by the patient must be documented in the source data.

### 9.2 Screening Period, Including Baseline and Enrollment

The Screening period is comprised by Screening and Baseline visits which may be performed on the same day; in this circumstance, the visit must be completed within 21 days before Day 0. If the patient screen fails, document the reason(s) in the source data and on the Screening & Enrollment log.

Adverse events (AEs) will be assessed at every visit. Events occurring pre-first IMG-7289 dose will be recorded as Medical History; those occurring post first IMG-7289 dose through the EoS visit will be recorded as AEs.

**Note:** In the UK, serious AEs (SAEs) will be recorded from time of consent through the EoS **or** until the Investigator and Imago BioSciences determine that follow-up is no longer necessary.

### 9.2.1 Screening (Days -28 to Day -1)

- Review of all Inclusion and Exclusion Criteria
- Complete medical/medication history including:
  - 2016 WHO criteria for PMF (Section 16.2), or IWG-MRT recommended criteria for PPV-MF (Section 16.3) or PET-MF (Section 16.4).
  - Risk determination, using the IWG prognostic factors
  - Calculate ECOG performance status (Section 16.6)
  - History of all treatments for their current disease (including clinical course with ruxolitinib and/or other MF therapy) or any previous oncologic conditions; including chemical, surgical and/or radiotherapeutic
  - All concomitant medication, in addition to any used in the 15 days prior to Screening
  - Transfusion history, including: each RBC transfusion received with approximate volume and total units transfused over the 6 month period prior to Screening

**Note:** while on-study, any blood product transfusion received (RBC, platelets, etc.), with approximate volumes, and total units transfused will also be documented.

- Full PE, including Vital Signs – review of all body systems as indicated by signs/symptoms
- Height (without shoes)
- Full Local Laboratory Assessment

**Note:** In Italy, HIV, HBsAg, HBsAb, HBcAb and HCV testing must also be performed.

- Urinalysis

**Note:** If Screening/Baseline **are not** occurring on the same day, then please refer to Section 9.2.2. If Screening/Baseline **are** occurring on the same day, then the following are required at Screening:

- Germline sample(s) for Central Laboratory genomic analysis
- Blood samples for Central Laboratory genomic analysis\*
- Bone Marrow Sampling\*
- Schedule MRI or CT (if patient is not a candidate for MRI) for pre-dose Day 0 ± 2 days
- Provide patient with multiple copies of the MPN-SAF TSS **24-HOUR RECALL** tool and instruct patient to complete the questionnaire daily for 7 consecutive days beginning on Day -6 and ending pre-dose Day 0.

\*If possible, bone marrow and blood sampling for genomic analysis should be performed on the same day.

### 9.2.2 Baseline Period (Days -21 to Day -1) and Enrollment

If Screening and Baseline visits are conducted on separate days, then the following are required at the Baseline visit:

- Limited PE, including vital signs
- Full Local Laboratory Assessment
- Urinalysis

- Germline sample(s) for Central Laboratory genomic analysis
- Blood samples for Central Laboratory genomic analysis\*
- Provide patient with multiple copies of the MPN-SAF TSS **24-HOUR RECALL** tool and instruct patient to complete the questionnaire daily for 7 consecutive days beginning on Day -6 and ending pre-dose Day 0
- Bone Marrow Sampling\*
- Schedule MRI or CT (if patient is not a candidate for MRI) for pre-dose Day 0 ( $\pm 2$  days)

**Note:** In Germany, use of computerised tomography (CT) is not permitted for patients unable to undergo magnetic resonance imaging (MRI). Only MRI is permitted for study purposes.

\*If possible, bone marrow and blood sampling for genomic analysis should be performed on the same day.

### 9.2.3 Enrollment

For eligibility purposes, the following should be reviewed and/or confirmed:

- History of recent surgical procedures
- Recent use of investigational drugs
- Laboratory results, including historical laboratory values, will be assessed by the Principal Investigator (PI) before enrollment. Any deviation in laboratory values that are confirmed on re-examination to be clinically significant by the PI and that would jeopardize the safety of the patient or impact on the validity of the study results will result in exclusion of that patient.

Once Screening/Baseline procedures have been performed and it is confirmed that the patient can be enrolled, patients will be enrolled in accordance with procedures detailed in the Study Reference Manual.

If the patient screen fails during this time, document the reason(s) in the patient's source data and on the Screening & Enrollment log.

### 9.2.4 Last Day of Screening Period (Day -1)

On Day -1 the study coordinator will contact the patient and remind them to:

- Report to the clinic the following day at the agreed time
- Not eat for at least 1 hour prior to dosing as IMG-7289 is to be taken on an empty stomach

## 9.3 Initial Treatment Period (ITP)

Procedures are presented below for each visit by assessments performed pre-dose, at dosing, and post-dose (as applicable).

### 9.3.1 ITP Day 0 – Treatment Start

#### 9.3.1.1 ITP Pre-Dose Day 0

- Update medical/medication history with any changes since Screening
- Limited PE, including Vital Signs

- Collect the completed copies of the MPN-SAF TSS, and provide patient with the MPN-SAF TSS **7-DAY RECALL** tool for completion prior to arriving for, or at their Day 7 visit
- Full Local Laboratory Assessment
- Urinalysis

CCI

- Perform abdominal MRI (or CT if the patient is not a candidate for MRI) within a  $\pm 2$  day window
- Dispense doses sufficient until the next visit and provide Dosing Instructions
- Ensure patient continues to meet eligibility criteria prior to dosing

**Note:** In Germany, use of computerised tomography (CT) is not permitted for patients unable to undergo magnetic resonance imaging (MRI). Only MRI is permitted for study purposes.

#### 9.3.1.2 ITP Dosing Day 0

- Administer Study Drug

#### 9.3.1.3 ITP Post-Dose Day 0

- Patients should remain in clinic for at least 2 hours post first dose
- Query for Adverse Events, using non-directive questions (i.e., "How are you feeling")
- Schedule Day 7 clinic visit

#### 9.3.2 ITP Weekly Visits - Days 7, 14, 21, 28, 35, 42, 49 and 56 ( $\pm 2$ days)

- Limited PE, including Vital Signs
- Adverse Events and Concomitant Medications
- Collect MPN-SAF TSS and provide the MPN-SAF TSS **7-DAY RECALL** tool to patient for completion prior to arriving for, or at the next visit
- Pre-dose: Perform haematology assessment and determine if dose titration is required in accordance with:
  - **Amendment 6 patients:** Refer to Section 7.2.3.2, and utilize:
    - **Table 2** for Days 7, 14 and 21
    - **Table 3** for Day 28 and onward
  - **Continuing Amendment 5\* patients:** Refer to Section 7.2.3.1, and utilize:
    - **Table 1**
- Pre-dose: Perform drug accountability and collect study medication
- Dispense doses sufficient until the next visit and provide Dosing Instructions
- Schedule next clinic visit

\*Amendment 5 patients must complete the Initial Treatment Period and transition to Amendment 6 titration and re-challenge rules upon commencing the Additional Treatment Period.

### 9.3.2.1 ITP Days 7, 21, 35, 42 and 49 only

- Pre-dose: Blood sample for haematology

### 9.3.2.2 ITP Day 14 only

- Pre-dose: Blood sample for haematology
- Pre-dose: Blood sample for Central Laboratory cytokine analysis

### 9.3.2.3 ITP Day 28 only

- Pre-dose: Full Local Laboratory Assessment
- Pre-dose: Blood sample for Central Laboratory cytokine analysis

### 9.3.2.4 ITP Day 56 only

- Pre-dose: Full Local Laboratory Assessment
- Provide extra copies of the MPN-SAF TSS **7-DAY RECALL** tool to patient sufficient until the next visit (for completion during the 'off' week, Day 63 and prior to arriving for, or at the Day 70 visit)

### 9.3.3 ITP Bi-Weekly Visits - Days 70, 84, 98 and 112 ( $\pm 2$ days)

**Note:** It is anticipated that by Week 8 patients will have achieved a stable dose, with weekly visits no longer necessary. For the exceptional patient whose dose has not stabilized, weekly visits may continue at the PI's discretion. For such patients, the following is required at each weekly visit:

- Pre-dose: Blood sample for haematology
- Pre-dose: Perform haematology assessment and determine if dose titration is required in accordance with:
  - **Amendment 6 patients:** Refer to Section 7.2.3.2, and utilize:
    - **Table 3**
  - **Continuing Amendment 5\* patients:** Refer to Section 7.2.3.1, and utilize:
    - **Table 1**

All other patients will undergo the following at bi-weekly visits:

- Limited PE, including Vital Signs
- Adverse Events and Concomitant Medications
- Collect MPN-SAF TSS and provide extra copies of the MPN-SAF TSS **7-DAY RECALL** tool to patient sufficient until the next visit (for completion during each 'off' week, i.e., Days 77, 91 and 105 and prior to arriving for, or at the next visit)
- Pre-dose: Perform haematology assessment and determine if dose titration is required in accordance with:
  - **Amendment 6 patients:** Refer to Section 7.2.3.2, and utilize:
    - **Table 3**
  - **Continuing Amendment 5\* patients:** Refer to Section 7.2.3.1, and utilize:
    - **Table 1**

- Perform drug accountability and collect study medication
- Dispense doses sufficient until the next visit and provide Dosing Instructions
- Schedule next clinic visit

\*Amendment 5 patients must complete the Initial Treatment Period and transition to Amendment 6 titration and re-challenge rules upon commencing the Additional Treatment Period.

#### 9.3.3.1 ITP Days 70 and 98 only

- Pre-dose: Blood sample for haematology

#### 9.3.3.2 ITP Day 84 only

- Pre-dose: Full Local Laboratory Assessment
- Pre-dose: Urinalysis
- Pre-dose: Blood sample for Central Laboratory genomics (all sites), cytokine (all sites), HbF and %F cell (US sites only) analysis
- Perform abdominal MRI (or CT if patient is not a candidate for MRI ( $\pm 7$  days))

**Note:** In Germany, use of computerised tomography (CT) is not permitted for patients unable to undergo magnetic resonance imaging (MRI). Only MRI is permitted for study purposes.

#### 9.3.3.3 ITP Day 112 only

- Pre-dose: Full Local Laboratory Assessment
- Provide extra copies of the MPN-SAF TSS **7-DAY RECALL** tool to patient sufficient until the next visit (for completion during each 'off' week, i.e., Days 119, 126 and 133 and prior to arriving for, or at the next visit).

#### 9.3.4 ITP Monthly Visits - Days 140 and 168 ( $\pm 3$ days)

**Note:** It is anticipated that by Week 20 patients will have achieved a stable dose, with bi-weekly visits no longer necessary. For the exceptional patient whose dose has not stabilized, bi-weekly visits may continue at the PI's discretion. For such patients, the following is required at each bi-weekly visit:

- Pre-dose: Blood sample for haematology
- Pre-dose: Perform haematology assessment and determine if dose titration is required in accordance with:
  - **Amendment 6 patients:** Refer to Section 7.2.3.2, and utilize:
    - **Table 3**
  - **Continuing Amendment 5\* patients:** Refer to Section 7.2.3.1, and utilize:
    - **Table 1**

All other patients will undergo the following at monthly visits:

- Limited PE, including Vital Signs
- Adverse Events and Concomitant Medications
- Collect MPN-SAF TSS and provide extra copies of the MPN-SAF TSS **7-DAY RECALL** tool to patient sufficient until the next visit (for completion during each “off” week, i.e., Days 147, 154 and 161 and prior to arriving for, or at the next visit)
- Pre-dose: Full Local Laboratory Assessment
- Pre-dose: Perform haematology assessment and determine if dose titration is required (necessary at Day 168 only if patient is continuing to ATP) in accordance with:
  - **Amendment 6 patients**: Refer to Section 7.2.3.2, and utilize:
    - **Table 3**
  - **Continuing Amendment 5\* patients**: Refer to Section 7.2.3.1, and utilize:
    - **Table 1**
- Perform drug accountability and collect study medication
- Dispense doses sufficient until the next visit and provide Dosing Instructions (necessary at Day 168 only if patient is continuing to ATP)
- Schedule next clinic visit

\*Amendment 5 patients must complete the Initial Treatment Period and transition to Amendment 6 titration and re-challenge rules upon commencing the Additional Treatment Period.

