#### *Initial Treatment Period (ITP):*

**Note:** Please refer to Section 7.2.3.1 for patients currently being treated under Amendment 5

For patients commencing treatment under Amendment 6, treatment will begin on Day 0 at the new  $D_s$  of 0.6 mg/kg QD. In association with this increased starting dose, the first up-titration is not permitted until Day 28. Extending the time to first up-titration from Day 14 to Day 28 is supported by the observation that the time needed to reach a stable platelet count is between 3 and 4 weeks; additionally, this approach minimizes the risk of severe thrombocytopenia for the few patients who may require less than 0.6 mg/kg/dCCI

[REDACTED]

The platelet titration target expected to be associated with a clinically significant therapeutic effect is:

- A platelet count of  $\geq 50$  to  $\leq 75$  k/ $\mu$ L ( $50-75 \times 10^9/L$ ).

Please refer to Section 7.2.3.2 for additional information on the dosing of Amendment 6 patients.

*Additional Treatment Period (ATP):* Qualifying patients will 're-start' IMG-7289 on ATP Day 0, with dose titration continuing as *per* the Titration Rules in **Table 3**; there should be no interruption in dosing (i.e., Day 168 = Day 0 of new ATP). Additional dose-titration may occur in consultation with the Medical Monitor.

**Study Duration:** CCI

the anticipated duration of participation in the study is expected to be at least 32 weeks from first patient-first visit (FPFV) to last patient-last visit (LPLV). Additional treatment may be given, contingent on an assessment of patient benefit.

**Study Assessments:** The assessments outlined below are presented in detail by study visit in Section 9, and in the Schedule of Assessments Sections 16.1).

The Myeloproliferative Neoplasm Symptom Assessment Form Total Symptom Score (MPN-SAF TSS) will be used. The 24-HOUR RECALL tool (Appendix 16.8) will be completed daily for the 7 days preceding first dose (Days -6 to pre-dose Day 0) during Baseline. The 7-DAY RECALL tool will be completed weekly from Day 7 through the EoS Visit (Appendix 16.9). Multiple questionnaires will need to be provided to patient for completion between visits as visit schedule decreases over time.

Adverse events (AEs) will be assessed at every visit post first IMG-7289 dose through the EoS visit.

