, following the first dose, no up-titrations may be made until ITP Day 28, and thereafter, no more frequently than every three weeks. Prolonging the time to first up-titration from ITP Day 14 to ITP Day 28 also minimizes the risk of severe thrombocytopenia for the few patients who may require less than 0.6 mg/kg/d. In conjunction with the increased starting dose and the longer intervals between up-titrations, the incremental dose titrations have been decreased. By allowing 21 days for equilibration of the platelet count to a *new* dose, combined with smaller dose titrations, it is expected patients will be subject to fewer fluctuations in both dose and platelet counts. This is also expected to provide more consistent exposure to drug with the effect of enhancing the clinical benefits.

In summary, *per* the dosing changes undertaken with this amendment, in association with the increased starting dose of 0.6 mg/kg/d,CCI

while **down-titrations** can be made at any time in the best interests of the patient. Titration and re-challenge rules specific to ITP Days 7, 14 and 21 have been generated to instruct whether patient doses should be maintained or down-titrated (**Table 2**), with a second set of rules specific to ITP Day 28 and onward (**Table 3**).

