#### **7.2.4 Dosage: Additional Treatment Period**

For all patients entering a new Additional Treatment Period, dose titration will be per the Titration Rules in **Table 3**. Additional dose-titration may occur in consultation with the Medical Monitor.

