##### 9.4.1 ATP Day 0 - Treatment 'Re-start'

###### 9.4.1.1 Day 0

All assessments should ideally be performed pre-dose; however, with the exception of the haematology blood test and determination of the need for a dose titration, the assessments may be performed post-dose if needed.

The below assessments do not need to be repeated if performed on the same or calendar day prior.

- Verify patient meets the criteria for additional treatment
- Limited PE, including Vital Signs
- Adverse Events and Concomitant Medication
- Collect MPN-SAF TSS and provide extra copies of the MPN-SAF TSS **7-DAY RECALL** tool to patient sufficient until the next visit (for completion during each 'off' week, i.e., Days 7, 14 and 21 and prior to arriving for, or at the next visit)
- Pre-dose: Full Local Laboratory Assessment
- Urinalysis
- Pre-dose: Perform haematology assessment and determine if dose titration is required according to **Table 3** in Section 7.2.3.2\*

- Dispense doses sufficient until the next visit and provide Dosing Instructions
- Administer Study Drug, if appropriate, based on patient's routine dosing time
- Schedule next clinic visit

\*Amendment 5 patients starting a new ATP Day 0 after re-consenting to Protocol Amendment 6 will be treated under Amendment 6 titration and re-challenge rules.

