#### 9.4.2 ATP Days 28, 56, 84, 112, 140 and 168 ( $\pm 4$ days)

**Note:** It is anticipated that patients continuing in the ATP will have already achieved a stable dose, with bi-weekly visits no longer necessary. For the exceptional patient whose dose has not stabilized, bi-weekly visits may continue at the PI's discretion. For such patients, the following is required at each bi-weekly visit:

- Pre-dose: Blood sample for haematology
- Pre-dose: Perform haematology assessment and determine if dose titration is required in accordance with:
  - **Amendment 6 patients:** Refer to Section 7.2.3.2, and utilize:
    - **Table 3**
  - **Continuing Amendment 5\* patients:** Refer to Section 7.2.3.1, and utilize:
    - **Table 1**

All other patients will undergo the following at monthly visits.

- Limited PE, including Vital Signs
- Adverse Events and Concomitant Medications
- Collect MPN-SAF TSS and provide extra copies of the MPN-SAF TSS **7-DAY RECALL** tool to patient sufficient until the next visit (for completion during each 'off' week, i.e., Days 35, 42, 49, etc. and prior to arriving for, or at the next visit)
- Pre-dose: Full Local Laboratory Assessment
- Pre-dose: Perform haematology assessment and determine if dose titration is required (necessary at Day 168 only if patient is continuing in ATP) in accordance with:
  - **Amendment 6 patients:** Refer to Section 7.2.3.2, and utilize:
    - **Table 3**
  - **Continuing Amendment 5\* patients:** Refer to Section 7.2.3.1, and utilize:
    - **Table 1**
- Perform drug accountability and collect study medication
- Dispense doses sufficient until the next visit and provide Dosing Instructions (necessary at Day 168 only if patient is continuing in ATP)
- Schedule next clinic visit

\*Amendment 5 patients must complete the Treatment Period they are currently being treated under in accordance with the Amendment 5 titration and re-challenge rules and will transition to the Amendment 6 rules upon commencing a new Additional Treatment Period.

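### For Amendment 5 patients entering a new ATP, the single titration decision on Day 168, which is also ATP Day 0, is assigned to Table 1 by Sections 9.3.4 and 9.4.2 and to Table 3 by Sections 7.2.4, 9.4 and 9.4.1.1

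*Protocol*

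**What the plan says.** Protocol Section 9.3.4 covers ITP Days 140 and 168. Its titration bullet tells sites to "determine if dose titration is required (necessary at Day 168 only if patient is continuing to ATP) in accordance with" one of two tables. For continuing Amendment 5 patients the instruction is "Refer to Section 7.2.3.1, and utilize" Table 1. The footnote reads "Amendment 5 patients must complete the Initial Treatment Period and transition to Amendment 6 titration and re-challenge rules upon commencing the Additional Treatment Period".

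Section 9.4.2 has a near-identical bullet for ATP visits: "Perform haematology assessment and determine if dose titration is required (necessary at Day 168 only if patient is continuing in ATP) in accordance with", again with Table 1 for continuing Amendment 5 patients. Its footnote moves them to the Amendment 6 rules when a new ATP begins.

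The Synopsis ties the two periods together: "there should be no interruption in dosing (i.e., Day 168 = Day 0 of new ATP". Section 5.1.2 states the same identity.

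For the start of an ATP, Section 7.2.4 says "For all patients entering a new Additional Treatment Period, dose titration will be per the Titration Rules in" Table 3. Section 9.4 names Table 3 for Amendment 5 patients who have re-consented to Amendment 6, from the start of their next ATP, and Table 1 up to that point. Section 9.4.1.1 names Table 3 for the pre-dose decision on ATP Day 0; its footnote also refers to re-consent. The same section states: "The below assessments do not need to be repeated if performed on the same or calendar day prior".

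**The concern.** A site treating an Amendment 5 patient at this transition has one pre-dose blood count and one dose to set. Read from the Day 168 visit, the protocol names Table 1. Read from the ATP Day 0 visit, it names Table 3. Section 9 describes itself as the main guidance for study visits, and both instructions sit inside it, so that statement gives neither one precedence.

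At stake is a dosing instruction that two careful sites could follow differently. The two rule sets are not the same: Section 3.6.1 says that under Amendment 6 "the incremental dose titrations have been decreased" and that the intervals between up-titrations are longer.

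**Working it through.** No power or sample-size figure is involved. The check is a day count and a side-by-side reading.

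1. **Is it the same day?** Section 7.2.3 gives 169 days of ITP dosing starting on Day 0. Day 0 to Day 168 inclusive is 168 − 0 + 1 = 169, so Day 168 is the last ITP dosing day. The Synopsis and Section 5.1.2 equate it with ATP Day 0. The dose that day is both the 169th of the ITP and the first of the ATP.

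2. **Is it the same decision?** In Section 9.3.4 the Day 168 titration step applies only to patients going on to the ATP, and the Day 168 dispensing step carries the same condition. A patient who stops has no titration decision that day. At Day 168 the bullet therefore exists only to set the ATP dose.

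3. **Which table for an Amendment 5 patient?**
   - Section 9.3.4, Day 168 bullet: Table 1
   - Section 9.4.2, Day 168 bullet: Table 1
   - Section 7.2.4: Table 3, for all patients entering a new ATP
   - Section 9.4: Table 3 once the next ATP starts, Table 1 before; re-consented patients
   - Section 9.4.1.1: Table 3; the footnote refers to re-consented patients

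4. **Does another provision decide it?** The footnotes to 9.3.4 and 9.4.2 switch rules when the ATP commences, but Day 168 is that day. Section 9.3.4.1 lets the patient enter the ATP once the Day 168 visit is complete, and Section 9.3.4.2 then sends the site to Section 9.4. This can be read as two steps: Day 168 closes under Table 1, then Day 0 opens under Table 3. It can also be read as placing the one decision inside the Day 168 visit. The no-repeat line in 9.4.1.1 does not settle this, because the titration determination is among the items listed below it and that item names Table 3. Whether a Table 1 determination made that day counts as having performed it is not stated.

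5. **How often, and for how many?** After the switch a patient follows Table 3. The overlap therefore occurs at most once per patient, at the end of whichever period was under way. The number affected is not given. About 75 − 18 = 57 patients would be in Phase 2b on the SAP's figures, but that includes patients from Amendments 4 and 6, so it is only a loose ceiling.

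6. **Would the dose differ?** Tables 1 and 3 are redacted, so this cannot be determined. Section 3.6.1 limits later up-titrations under Amendment 6 to one every three weeks. On nominal monthly visits the gap from Day 140 is 168 − 140 = 28 days, more than 21, so that limit would not block a change. For a patient still on bi-weekly visits and up-titrated 14 days before, it could. Otherwise the known difference is the smaller increment, which matters only if the counts call for a change that day.

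**The case against.** The strongest case is that the order of events resolves the matter. The site completes Day 168, goes to Section 9.4, and opens ATP Day 0 under Table 3. Section 7.2.4, Section 9.4, Section 9.4.1.1 and both footnotes name the Amendment 6 rules for a new ATP. The item listed in 9.4.1.1 is specifically a Table 3 determination, so a Table 1 determination would not satisfy it. Section 7.2.3.1, to which the Table 1 line refers, is redacted and may itself state the transition rule.

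Much of this stands: the text leans one way. But it leaves in place a Table 1 instruction for a Day 168 decision whose only purpose is the ATP dose. If the sequence is meant to control, that line needs changing; if it is not, the other sections do.

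Several stronger readings are tempting, and the documents do not support them.

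- **That the conflict recurs at every ATP Day 168.** It does not, because the patient is on Table 3 after the first switch.
- **That it raises the risk of severe thrombocytopenia.** Section 3.6.1 ties that risk to delaying the first up-titration from ITP Day 14 to Day 28 after starting treatment, not to patients completing a 169-day period. Down-titration is allowed at any time.
- **That it biases ATP spleen results.** The first scheduled ATP scan is at ATP Day 168, after five further scheduled titration visits (Days 28, 56, 84, 112 and 140). The change of rules between periods is deliberate for these patients.
- **That a new eCRF field is needed to trace the doses.** Section 7.2.1 puts the dose in mg on each prescription, and SAP Section IX.A lists exposure data by patient.

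**Conclusion.** The contradiction is real and sits in the operative text. For an Amendment 5 patient moving into a new ATP under Amendment 6 after re-consent, one titration decision is assigned to two tables. A related inconsistency is that Section 7.2.4 speaks of all patients, while Section 9.4 and the 9.4.1.1 footnote speak of those who have re-consented.

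Its extent is limited to one decision per patient, in an unstated number of patients. A reader might infer that sites will give different doses. The visible text shows only that they could, where the tables differ for that patient's counts. The conclusion assumes that redacted Section 7.2.3.1 does not already resolve the transition, and that Day 168 and ATP Day 0 fall on one day, as the Synopsis and Section 5.1.2 state. This is worth correcting because it concerns a dosing instruction. No effect on the trial's analyses has been shown.

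**What to change.** Reconcile the Day 168 lines of Sections 9.3.4 and 9.4.2 with Sections 7.2.4, 9.4 and 9.4.1.1, so that one named table governs the Day 168 / ATP Day 0 decision for Amendment 5 patients. In the same edit:

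- state in 9.4.1.1 whether a titration determination made as part of the Day 168 visit serves as the ATP Day 0 determination;
- align the all-patients wording in 7.2.4 with the re-consent wording in 9.4 and 9.4.1.1.

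The choice of table belongs to the sponsor's clinical team; no view is taken here. The cost is about a sentence in each affected section, or a clarification letter to sites. It needs no new visits, patients or data fields.
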